6.4 Randomization

Participants who complete all baseline assessments will be randomized in a 1:1 fashion to either BBTI plus eszopiclone or BBTI using a stratified permuted block randomization scheme. The proposed assignment method has been shown to effectively create similar groups of participants across treatment conditions ⁹. The randomization list will be generated by the study biostatistician. Subjects will be included in data analyses according to their randomized assignment irrespective of the treatment received (intent-to-treat).

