Our primary strategy is to compare BBTI plus eszopiclone versus BBTI using analyses that are straightforward and highly interpretable while still accounting for other important covariates. Within-subject changes in the PSQI from baseline will be **the primary outcome**. The primary analyses involve the statistical assessment of group differences with regards to this outcome and will be based on a linear model. In taking this approach, we fit the dependent variable as a linear function of independent variables treatment regimen, and baseline outcome level. Rather than utilizing the null distribution associated with the classic F-test for treatment differences within this framework which is dependent on the validity of distributional assumptions, an exact permutation testing approach will be utilized. The randomization mechanism at work is a crucial component in this study in that it will be used to create the randomization distribution by which statistical significance will be determined. For more on this approach see Gail, Tan, and Piantadosi (1988)²⁴. Reported p-values will be obtained from the permutation distributions of the test statistics based on 10,000 Monte Carlo simulations. As secondary analyses, additional subject covariates will be included as independent variables. The interaction of the treatment group and subject covariates may also be examined in a secondary fashion in order to identify possible differential effects of treatment. All statistical tests will be two-sided and tested at a 0.05 nominal significance level.

Analysis plan for the secondary outcomes

Analyses of secondary outcomes will proceed in a similar fashion. For actigraphy outcomes, data will be averaged over one-week periods. Alpha level will be adjusted using the Bonferroni correction when indicated. All analyses will be carried out using SAS version 9.4 (or higher) statistical software (Cary, NC).

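### The primary model omits the randomization strata: the permutation test stays valid, but precision is given up if the strata predict PSQI change beyond baseline

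*Combined protocol and SAP*

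**What the plan says.** Section 6.4 (Randomization) allocates 1:1 to "BBTI plus eszopiclone or BBTI using a stratified permuted block randomization scheme". Neither the stratification factors nor the block size is given anywhere in the document.

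Under the heading Analysis plan for the primary outcome, the outcome is change in PSQI, and the model is described thus: "we fit the dependent variable as a linear function of independent variables treatment regimen, and baseline outcome level". Everything else is deferred: "As secondary analyses, additional subject covariates will be included as independent variables".

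The same paragraph sets aside the classical F-test null distribution. Instead "an exact permutation testing approach will be utilized", and of the randomization mechanism it says that "it will be used to create the randomization distribution by which statistical significance will be determined". P-values come from 10,000 Monte Carlo draws. The paragraph does not say in so many words that the draws are made within strata and blocks, and it gives no method for a confidence interval. Secondary outcomes are to be handled in a similar way.

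**The concern.** Stratifying the randomization balances the arms on factors thought to be prognostic. If those factors do predict the outcome, the gain reaches the analysis only when the analysis knows about them. A model with treatment and baseline PSQI alone leaves the between-stratum variation in the residual, so its standard error describes a less precise trial than the one that was run.

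Dropout adds a second loss. Complete blocks keep the arms balanced within each stratum, and then even an estimate without strata terms benefits. Once a quarter of patients are lost, part of the imbalance returns and only a model term can remove it.

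At stake is a few points of power in a trial planned at about 80%, and the width of any interval reported with the treatment effect.

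**Working it through.** **The plan's own figure.** Section 8.0 gives SD 3.5, difference 3, 21 per group, about 80% power; alpha is two-sided 0.05. The standard error is 3.5 × √(2/21) = 1.080. Then 3/1.080 − 1.96 = 0.82, and Φ(0.82) = 79.3%. The figure is reproduced by the normal approximation with SD 3.5 used directly (a t-test gives 77.4%).

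**Inputs for the check.** From Section 8.0: 52 enrolled and 25% dropout, so 52 × 0.75 = 39 completers; difference 3; residual SD 3.5. Section 8.0 also gives a baseline–post correlation of 0.7. If 3.5 is the SD of the raw score, the residual SD after baseline adjustment is 3.5 × √(1 − 0.49) = 2.5, so both values are considered. Assumed, because the document gives none: 2 or 4 strata, blocks of 4, random dropout, and strata explaining 0 to 30% of the variance of PSQI change that baseline PSQI leaves.

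**Standard error by formula.** With 39 completers split evenly, the SE without strata is 3.5 × √(2/19.5) = 1.12. With strata in the model it is about 1.12 × √0.8 = 1.00 at 20% explained and 1.12 × √0.7 = 0.94 at 30%, before the small loss for estimating extra terms.

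**Standard error by simulation (four strata, dropout included).** Without strata the model SE averages 1.14. The true SD of the estimate is 1.05–1.06 at 20% and 1.00–1.02 at 30%. The model SE is therefore too large by about 8–9% (1.14/1.06 to 1.14/1.05) and 12–14% (1.14/1.02 to 1.14/1.00). Nominal 95% intervals cover about 97%. With strata in the model, SE and SD agree (1.03 and 1.03; 0.96 and 0.96) and coverage is 95%.

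**Power for a difference of 3, residual SD 3.5, 39 completers** (4,000 trials per setting, 199 draws each, Monte Carlo error about 0.6–0.7 points):

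| Strata | Share explained | Free shuffle, strata omitted | Draws within strata and blocks, strata omitted | Draws within strata and blocks, strata in model |
|---|---|---|---|---|
| 2 | 20% | 74.2% | 78.1% | 80.7% |
| 2 | 30% | 72.8% | 80.3% | 85.0% |
| 4 | 20% | 73.9% | 77.8% | 79.5% |
| 4 | 30% | 72.8% | 80.0% | 84.8% |

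The step that concerns the planned test is from the fourth column to the fifth: 80.7 − 78.1 = 2.6, 85.0 − 80.3 = 4.7, 79.5 − 77.8 = 1.7 and 84.8 − 80.0 = 4.8 points. A separate run (3,000 trials, 399 draws) gave these changes for 2 and 4 strata:

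- 0% explained: −0.8 and −1.8
- 10%: +1.8 and −0.3
- 20%: +2.9 and +2.6
- 30%: +5.1 and +4.1

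At residual SD 2.5, power was already 94–98% and the change ran from −1.0 to +1.2 points.

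**Role of dropout.** With 42 patients and no dropout, adding strata to the within-strata test changed power by only about 0 to 1 point (at 30% explained, 87.4% to 88.6% with two strata and 88.7% to 89.9% with four). The larger gain above comes from the imbalance that dropout creates.

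**Validity.** With draws made within strata and blocks and strata omitted, null rejection stayed between 3.9% and 5.6% across all settings, with and without dropout. Free shuffling with dropout rejected about 2.6–3.5% of the time.

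**The case against.** The strongest reply is that the plan already handles this. The p-value does not use the model standard error, and a reference distribution built from the actual mechanism, which is stratified blocks, carries the stratification into the test. That stands. A reader might infer from the omitted strata that the primary test is invalid, or that power falls because the model standard error is too wide. The document supports neither: the test holds its level, and the remaining loss comes mainly from dropout. Nor does it support assuming that labels will be shuffled freely; it points the other way, though it should say so outright.

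It can also be said that no interval or standard error for the treatment effect is promised. True, so the point about width applies only if one is taken from the fitted model. No other method is offered, however, and an estimate will need one.

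Third, a reader might infer that power is lost whenever the strata predict PSQI change. That is too strong. Strata that act through baseline PSQI are already covered by the baseline term, and weak strata do not repay their degrees of freedom.

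Fourth, the plan speaks of accounting for important covariates, and of weighting if key baseline differences emerge. But the model as specified has only two terms, and weighting that depends on observed differences is no substitute for a prespecified stratum term. Random dropout, as simulated, causes no bias, so this remains a question of efficiency.

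**Conclusion.** The mismatch between Section 6.4 and the primary model is real, and its cost is in efficiency. The planned test is valid if its draws follow the stratified blocks; any error from omitting the strata is conservative.

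With 2 or 4 strata, blocks of 4, 39 completers and residual SD 3.5, adding the strata to a within-strata permutation test is worth about 2–3 points of power at 20% explained, 3–5 at 30% and about 0–1 at 10%. It costs up to about 1–2 points if the strata explain nothing. At residual SD 2.5 the change is within about 1 point either way. Shuffling that ignored the strata would give up about 4–7 further points at 20–30% explained and residual SD 3.5.

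Because the strata are not named, the explained share cannot be taken from the document. These figures are a range under assumptions and do not forecast this trial. The change is still worth making: it is cheap, it fits the analysis to the design, and it is credible only if specified in advance.

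**What to change.** Under Analysis plan for the primary outcome, name the stratification factors and make the primary model PSQI change on treatment, baseline PSQI and those factors as main effects. State that all 10,000 re-randomizations are drawn within the same strata and blocks as the trial's allocation. Use the same terms for the secondary outcomes. If a confidence interval is to be reported, say that it comes from this model.

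The cost is a sentence or two of text and no new data. In the analysis it uses one to three degrees of freedom, which means up to about 2 points of power if the strata turn out to be unrelated to the outcome.

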8.0 Sample size

The sample size selected for this study is based on the analysis of the primary outcome. For the sake of simplicity, calculations corresponding to the test based on the proposed approach are approximated by those of a simple two-sample t-test for mean differences. The estimate of the variability used for sample size calculations was derived from a randomized controlled trial of BBTI for the treatment of insomnia in military Veterans where an approximate standard deviation of 3.5 was found¹². A correlation between baseline and post-randomization measurements of the outcome of 0.7 was obtained from our data presented in the section of preliminary findings. Calculations show a sample size of 21 per group (42 total) will allow us to detect differences as small as 3 units (a minimal clinically important difference)²⁵ with approximately 80% power. The actual analysis is based on a model with additional independent variables that will account for some of the unexplained variability in the

dependent variable. These calculations may be viewed as conservative. Since we expect a 25% dropout rate, 52 patients will be enrolled in this study.

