Other (secondary) measures of CPAP adherence will include also average hours of use per night and usage index which will be calculated as the number of days the CPAP was used for more than 4 hours divided by the total number of days studied.

Statistical and Analytical Plans

Data analysis will consist of descriptive statistics of all variables and constructs. These will include counts and percentages for binary and categorical variables and means and standard deviations, or medians with lower and upper quartiles, for continuous variables, along with minimum and maximum values and counts of missing values. Data distributions and all model assumptions will be checked for all analyses. If model assumptions are not met, data will either be transformed or analyzed using a non-parametric test, as appropriate. The descriptive statistics will ensure that our randomization process is effective and that no statistical differences exist between the study population. In the event that key differences emerge, weighting procedures will be used in the analysis to control for these baseline differences. The intent-to-treat (ITT) protocol will be followed for these analysis²². We plan also on following up all participants enrolled in the study independent of whether they complete treatment so that we can perform both per protocol (PP) as well as intent-to-treat analyses. Per protocol analyses focus evaluation only on those individuals who complete treatment. The logic is that to evaluate the effectiveness of a treatment protocol, analyses should be conducted on those who received “full dose” of the treatment. By contrast, ITT analyses place greater emphasis on external validity and focuses on the real world impact of the treatment taking into account that individuals may choose to drop out of treatment because of the nature of the treatment itself. In ITT analyses, all respondents who are initially randomly assigned to the various experimental conditions are analyzed to the posttests²³ whereas in PP analyses, only those who complete the treatment protocol are analyzed. Both forms of analyses are informative, and we will approach the data from each perspective.

Analysis plan for the primary outcome

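### Enrolling 52 with 25% dropout leaves 39 evaluable participants, not the 42 behind the power statement; 42 would need 56 enrolled, or loss of no more than about 19%.

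*Combined protocol and SAP*

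**What the plan says.** Section 8.0 (Sample size) approximates the primary analysis by a two-sample t-test and says so. For variability it cites an earlier trial of the behavioral treatment in Veterans, in which "an approximate standard deviation of 3.5 was found". It also reports a baseline-to-follow-up correlation of 0.7 from preliminary data. It then states: "Calculations show a sample size of 21 per group (42 total) will allow us to detect differences as small as 3 units", "with approximately 80% power". The section describes these calculations as conservative and ends: "Since we expect a 25% dropout rate, 52 patients will be enrolled in this study".

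Two other sections bear on the point:

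- Under the analysis plan for the primary outcome, the outcome is within-subject change in PSQI, and "we fit the dependent variable as a linear function of independent variables treatment regimen, and baseline outcome level". The test level is also set there: "All statistical tests will be two-sided and tested at a 0.05 nominal significance level".
- Under Statistical and Analytical Plans: "We plan also on following up all participants enrolled in the study independent of whether they complete treatment".

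The documents give no other dropout rate, enrolment target or rule for replacing participants.

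**The concern.** The last sentence of section 8.0 presents 52 as the number that absorbs a 25% loss and still delivers the 42 used for power. Dropout is a fraction of those enrolled, so the required number is divided by one minus that fraction. The figure of 52 looks like the common slip of multiplying by one plus the fraction. If so, the stated power rests on more participants than the plan itself expects to have.

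The same paragraph makes the consequence hard to judge. It does not say whether 3.5 is the SD of a PSQI score or of its change, or whether the correlation of 0.7 entered the calculation. A reader therefore cannot work out the power of the baseline-adjusted model that will actually be fitted, at 42 or at any smaller number.

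**Working it through.** **Inputs.** From section 8.0: difference 3 units, SD 3.5, correlation r = 0.7, 21 per group, 25% dropout, 52 enrolled. From the primary-outcome analysis plan: two-sided 0.05. From section 6.4: 1:1 allocation.

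**1. The plan's 42.** The standard error of the difference is 3.5 × √(1/21 + 1/21) = 1.080, so the standardized difference is 3/1.080 = 2.777.
- Normal approximation: Φ(2.777 − 1.960) = 79.3%.
- Noncentral t, 40 degrees of freedom: 77.3%.

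The plan's figure is therefore reproduced approximately, with 3.5 entered directly and r unused. It is not in dispute.

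**2. The plan's 52.**
- Multiplying: 42 × 1.25 = 52.5, or 21 × 1.25 = 26.25 per group. Rounded down, this gives 52 (26 per group).
- Dividing: 42/(1 − 0.25) = 56 (28 per group).

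Only the first route gives 52.

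**3. What 52 delivers.**
- Remaining after 25% loss: 52 × 0.75 = 39, which is 3 fewer than 42 (about 19 and 20 per group).
- Largest loss that keeps 42: 52 − 42 = 10 participants, and 10/52 = 19.2%.

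**4. Effect on the plan's own t-test (SD 3.5, 3 units).** At 19 and 20, the standard error is 3.5 × √(1/19 + 1/20) = 1.121 and the standardized difference is 2.676.

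| Evaluable | Power, noncentral t | Power, normal | Detectable difference at 80% power (noncentral t) |
|---|---|---|---|
| 42 (21/21) | 77.3% | 79.3% | 3.10 units |
| 39 (19/20) | 74.1% | 76.3% | 3.23 units |

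Like for like, the loss is about 3 percentage points.

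**5. Effect on the planned baseline-adjusted test at 39.** This uses the noncentral t with one further degree of freedom spent on baseline, and assumes r = 0.7 and equal variances at baseline and follow-up.
- *If 3.5 is a score SD:* residual SD = 3.5 × √(1 − 0.7²) = 3.5 × √0.51 = 2.50. Power is 95%, and the detectable difference is about 2.3 units.
- *If 3.5 is the SD of change:* score SD = 3.5/√(2 × (1 − 0.7)) = 3.5/√0.6 = 4.52, and residual SD = 4.52 × √0.51 = 3.23. Power is 81% (84% at 42), and the detectable difference is about 3.0 units.

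**The case against.** The strongest reply is that the slip changes no decision. The section calls its calculation conservative, and under either reading of 3.5 the planned adjusted test still has about 80% power or more for 3 units at 39. The fall from 80% to 74% should not be charged to the inflation error either: most of it is already there at 42, where the noncentral t gives 77%. This stands, and it is why the point is not put as a threat to the trial. A conservative test still does not make 52 the right inflation of 42. If 3.5 is the SD of change, the margin at 39 is under one percentage point (80.6%).

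A second reply is that dropout may mean stopping treatment. The plan intends to follow those who stop and analyse everyone as randomized, so the number with outcomes could exceed 39 and approach 52. This is possible. But section 8.0 itself treats the 25% as a loss to be made up by enrolment, and the term is not defined. If 25% do stop treatment, 39 is the number left for the planned per-protocol analysis, which is limited to treatment completers.

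A third reply concerns the SD and the correlation. Since 21 per group follows from 3.5 entered directly, r was evidently not applied to it in the t-test. That seems right, but it does not show whether 3.5 was a score SD or a change SD in its source. This part is missing detail, secondary to the arithmetic. The 81% and 95% combine an SD from one source with a correlation from another, so they are illustrative until the inputs are defined.

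**Conclusion.** The concern holds. The enrolment target does not follow from the plan's own figures: 52 with 25% loss gives 39 evaluable, 42 would need 56 enrolled, and 52 protects 42 only up to a 19.2% loss. This takes dropout to mean having no PSQI outcome, which is how section 8.0 uses it.

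The size is modest: three evaluable participants and about 3 points of power in the plan's unadjusted t-test. The planned baseline-adjusted analysis is not shown to be underpowered, subject to the assumptions of r = 0.7 and equal variances. What needs correcting is one wrong number and inputs that are not fully defined. It should be corrected because the sample-size justification rests on it.

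**What to change.** Reword the paragraph in section 8.0:

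1. Keep 52 and do one of two things: state the expected evaluable number as 39 with its power, or state that 52 allows about 19% loss while retaining 42. If 42 evaluable at 25% loss is really intended, the target is 56.
2. Say whether dropout means stopping treatment or having no PSQI outcome, in line with the planned follow-up of those who stop.
3. State whether 3.5 is the SD of a PSQI score or of its change, and whether r = 0.7 is used.
4. Once those inputs are defined, give power for the baseline-adjusted test at 39: about 95% if 3.5 is a score SD, or about 81% if it is the SD of change, with the assumptions stated.

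The cost is one rewritten paragraph. Keeping 52 adds no participants and leaves treatment and analysis unchanged.
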